11.2.5 Gates MRI Scale Scores

Table 5: Gates MRI Ordinal Scale Clinical Endpoint Definitions

| Scale | Category | Endpoint definition |
|-------|---|---|
| 1 | Asymptomatic/symptoms similar to pre-COVID-19 status | 
 No symptoms and signs AND No limitation of daily activities |
| 2 | Mild | 
 Symptomatic AND No shortness of breath AND No hypoxemia (O_2 saturation $\geq 94\%$ in ambient air) |
| 3 | Moderate or severe | 
 Symptomatic AND Shortness of breath* OR tachypnea (respiratory rate ≥ 20 min)* OR hypoxemia ($< 94\%$ in ambient air)* |
| 4 | Critically ill | 
 Symptomatic AND Receiving high flow oxygen OR non-invasive mechanical ventilation |
| 5 | Critically ill with invasive mechanical ventilation or extra pulmonary complication | 
 Symptomatic AND Receiving invasive mechanical ventilation OR Life threatening or debilitating extra pulmonary complications |
| 6 | Critically ill with Extra-Corporeal Membrane Oxygenation (ECMO) | 
 Symptomatic AND Receiving ECMO |
| 7 | Death | 
 Death |

*For known COPD participants, moderate or severe category requires worsening of shortness of breath or medical or oxygen saturation from pre-COVID-19 status.

The distributions of the Gates MRI ordinal scale scores (defined as in Table 5) will be summarized by day and treatment group. Stacked bar plots presenting the proportion of participants in each category of Gates MRI ordinal scale at Days 8, 14, 21, and 28 for each treatment group will be provided.

11.2.6 WHO Ordinal Scale Scores

Table 6: WHO Ordinal Scale for Assessment of Clinical Status of COVID-19 Patients

| Participant Status | Descriptor | Scale |
|-------------------------------|--|-------|
| Uninfected | Uninfected; no viral RNA detected | 0 |
| Ambulatory mild disease | Asymptomatic; viral RNA detected | 1 |
| | Symptomatic; independent | 2 |
| | Symptomatic; assistance needed | 3 |
| Hospitalized moderate disease | Hospitalized; no oxygen therapy* | 4 |
| | Hospitalized; oxygen by mask or nasal prongs | 5 |

| | | |
|-----------------------------|--|----|
| Hospitalized severe disease | Hospitalized; oxygen by NIV or high flow | 6 |
| | Intubation and mechanical ventilation, pO ₂ /FiO ₂ ≥150 or SpO ₂ /FiO ₂ ≥200 | 7 |
| | Mechanical ventilation pO ₂ /FiO ₂ <150 (SpO ₂ /FiO ₂ <200) or vasopressors | 8 |
| | Mechanical ventilation pO ₂ /FiO ₂ <150 and vasopressors, dialysis, or ECMO | 9 |
| Dead | Dead | 10 |

WHO clinical progression scale; WHO Working group [WHO(c), 2020]
 ECMO=extracorporeal membrane oxygenation; FiO₂=fraction of inspired oxygen;
 NIV=non-invasive ventilation; pO₂=partial pressure of oxygen; RNA = ribonucleic acid; SpO₂=oxygen saturation.
 *If hospitalized for isolation only, record status as for ambulatory patient.

WHO ordinal scale scores (as defined in Table 6) will be summarized and analyzed for overall burden of disease and disease severity as similar to that described for Gates MRI scale scores. For the purposes of evaluating the disease severity using the proportional odds model, the log-odds of the cumulative probability of the WHO ordinal scale score ≤3 is modeled.

11.2.7 Incidence of Hospitalization

The proportion of hospitalized participants at any time up to and including Days 8, 14, 21, and 28 will be summarized for the study intervention and control with the corresponding 2-sided 95% CIs computed using the Mid-p method. The risk ratios and the corresponding 2-sided score 95% CIs associated with the incidence of hospitalization for the study intervention relative to control at any time up to and including Days 8, 14, 21, and 28 will be assessed using the stratified CMH method, stratified by number of days of symptoms at time of randomization (<6 days or ≥6 days).

11.2.8 Number of Days of Hospitalization

Number of days of hospitalization will be summarized using descriptive statistics by treatment group and number of days of symptoms at time of randomization (<6 days or ≥6 days).

11.3 Exploratory Analysis

11.3.1 SARS-CoV-2 Diagnostic Test

Proportion of participants having negative or positive SAR-CoV-2 diagnostic test will be summarized by treatment group and days since onset of symptoms at time of randomization (<6 days or ≥6 days) at Days 1, 4, 8, 14, 21, and 28. For computing percentages, the denominator will be the number of participants with a test outcome available or indicated as not done in CRF for a specific group and visit.

11.3.2 Cycle Threshold Value of SARS CoV-2 Test.

Cycle threshold value (Ct) is the number of cycles in an RT-PCR assay needed to amplify viral RNA to reach detectable level. Low Ct value represents the number of cycles in an RT-PCR assay needed to amplify viral RNA to reach a detectable level; with lower Ct values reflective of

higher viral levels. Ct will be summarized using descriptive statistics by treatment group and number of days since onset of symptoms at time of randomization (<6 days or ≥ 6 days) at Days 1, 4, 8, 14, 21, and 28.

Viral sequencing may be used to assess the phylogenetic relationships between SARS-CoV-2 viruses obtained from positive nasal swab samples. Phylogenetic trees will be generated to determine whether participants were part of a transmission cluster. The aforementioned analyses may be performed upon availability of SARS CoV-2 viral load data.

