## 2. Study Schedule of Procedures

**Table 1: Schedule of Activities**

Visits	Screening (≤5 days of Day 1)	Day 1	Day 4	Day 6	Day 8	Day 10	Day 12	Day 14	Day 18	Day 21	Day 24	Day 28	Day 35
Obtain consent	X												
Demographics, past and current medical history including known pregnancy/lactation status, and medication history	X												
Lab-confirmed SARS-CoV-2 positive diagnostic testing 	X												
Inclusion and exclusion criteria	X												
Concomitant medications	X	X	X	X	X	X	X	X	X	X	X	X	X
Randomization 	X												
Study intervention dose (Day 1 Day 21) and record adherence to dosing		X	X	X	X	X	X	X	X	X			
Clinical status assessment using ordinal scales for Gates MRI and WHO		X	X	X	X	X	X	X	X	X	X	X	X
COVID-19 signs and symptoms, temperature, oxygen saturation		X	X	X	X	X	X	X	X	X	X	X	X
AEs assessment	X	X	X	X	X	X	X	X	X	X	X	X	X
Bleeding events and severity assessment		X	X	X	X	X	X	X	X	X	X	X	X
Self-collection of nasal or oropharynx SARS-CoV-2 sample for diagnostic testing 	(X) 	X	X		X			X		X		X	

Note that visits will preferably take place remotely (refer to [Section 8](#)).

SARS-CoV-2= Severe acute respiratory syndrome coronavirus 2

Gates MRI= Bill & Melinda Gates Medical Research Institute

WHO = World Health Organization

 If there is documented positive SARS-CoV-2 diagnostic testing performed with a sample collected ≤10 days prior to screening, the test does not need to be performed. If no documentation, the potential participant will be asked to collect a nasal or oropharynx swab sample to send for testing.

 If documentation of a previous positive SARS-CoV-2 test is not available and a test is performed at screening, randomization will occur after a positive result is obtained.

 Participant will be asked to collect a sample per kit instructions. Discontinue collection during hospitalization and/or per physician's discretion when two consecutive negative results are available at any time during the study.

Note that an unscheduled visit may be required. Additional collection of a nasal swab sample may be performed based on the clinical judgement of the PI.

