#### **9.4.1. Nasal Sampling**

Nasal sampling for SARS-CoV-2 diagnostic testing will follow study instruction document from the testing laboratory. Nasal sampling collection will be discontinued during hospitalization and/or, per physician's discretion, when two consecutive negative results are available at any time during the study.

Instructions on handling, storage and shipment or delivery of nasal swabs that are collected by the participant will be provided to the participant and explained during the visit.

Additional nasal swab collection may be performed based on the clinical judgement of the PI or designee.

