4. INTRODUCTION

The purpose of this statistical analysis plan is to describe the framework for the reporting, summarization and statistical analysis methodology of the safety and efficacy parameters measured for the Gates Medical Research Institute (MRI) study COD-01-T01-01. It is based on Protocol Gates MRI - COD-01-T01-01 Version 4, Amendment 2, 27 January 2021. This study is performed as part of an adaptive, randomized platform core protocol for treatment of early and mildly symptomatic individuals in out-patient settings with severe acute respiratory syndrome coronavirus 2 (SARS-CoV-2) infection. Additional statistical analysis plans will be developed for future protocols and interventions that will be added to the core protocol.

On January 28 and February 3, 2021, the Independent Data Monitoring Committee (IDMC) met to review the available safety and efficacy data to (1) perform the monthly safety review of accumulating data; and (2) evaluate the results of the first prespecified interim analysis for futility. Based on the review of the data, the IDMC determined on February 3, 2021, that the futility boundary was crossed and recommended that the clinical study be stopped. The final statistical analysis plan was amended to reflect changes to the planned analysis following early termination of the study.

As of February 4, 2021, the following changes were made in the study conduct:

- all randomization is ceased and no new study participants are enrolled.
- current participants must discontinue dosing of all study drug and discard their study drug.
- participants should remain in active, masked follow up and continue their study visits until Day 35 if they have had at least one dose of study drug.
 - Participants who have not reached Day 21 will continue safety follow up only until Day 35. These participants will be monitored for AEs, bleeding events and concomitant medication. These participants will not have further assessments for Gates MRI and WHO ordinal scale, symptoms, and nasal swabs for polymerase chain reaction (PCR) test.
 - Participants who have reached Day 21 but not Day 35 of study will continue safety and efficacy follow up until Day 35. These participants will be monitored for AEs, bleeding events, concomitant medication, Gates MRI and WHO ordinal scales, and symptoms. These participants will not have further nasal swabs for PCR test.
- participants who have not yet taken any study drug will discontinue the study early.

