9.2 General Conventions

Frequency (n) and percentages (%) will be used to summarize categorical variables; mean, standard deviation (SD), median, minimum, and maximum will be used to summarize continuous variables.

Decimal precision for summary statistics of continuous variables will be based on the mean value. Typically, the mean will contain 1 more decimal place than actual values but the decimal precision may vary in order to obtain an organized and understandable table or listing. The median will contain the same number of decimal places as the mean, the SD will contain 1 more decimal place than the mean, and the minimum and maximum will contain 1 less decimal place than the mean.

Unless otherwise specified, the denominators for percentages will be the number of participants in each intervention group with non-missing data for the variable of interest.

The day of receiving first dose of study intervention is defined as Study Day 1 or Day 1. All other study days will be computed relative to Day 1. For events on or after Day 1, study day for a particular event or visit will be calculated as $\text{Date}_{\text{event}} - \text{Date}_{\text{Day 1}} + 1$. For events before Day 1, study day for a particular event will be calculated as $\text{Date}_{\text{event}} - \text{Date}_{\text{Day 1}}$. Day 0 will not be used.

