9.5 Handling of Missing Data

Missing and partial dates of prior and concomitant medications and adverse events will be imputed to determine the relationship between the start date of the event and the first dose date of study drug. The imputation rules provided in Appendices 2 and 3.

Statistical methods to address missing data for efficacy endpoints are provided in Section 11.

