11.2.3 Proportion of Participants with Disease Resolution

The proportions of participants who achieve disease resolution defined as symptom resolution at Days 8, 14, 21, and 28 will be summarized for the study intervention and control. The 2-sided 95% CI for the proportion will be computed using the Mid-p method. The absolute difference in the proportion and the corresponding 2-sided 95% CI of participants achieving disease resolution defined as symptom resolution at any time up to and including Days 8, 14, 21, and 28 between the study intervention and control will be assessed using the stratified Miettinen and Nurminen method, stratified by number of days of symptoms at time of randomization (<6 days or ≥ 6 days).

In addition, the proportions of participants who achieve disease resolution defined as symptom resolution and viral clearance (2 consecutive negative diagnostic tests) at any time up to and including Days 8, 14, 21, and 28 will be summarized and analyzed as similar to that described for the proportions of participants who achieve disease resolution defined as symptom resolution only.

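### Exploratory swab table (SAP 11.3.1): if swabs stopped after two negatives are coded not done, percent negative is understated by the share who stopped

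*SAP*

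**What the plan says.** SAP 11.3.1 is an exploratory, descriptive summary: "Proportion of participants having negative or positive SAR-CoV-2 diagnostic test will be summarized by treatment group" and by symptom-duration stratum, at Days 1, 4, 8, 14, 21 and 28. For the percentages, "the denominator will be the number of participants with a test outcome available or indicated as not done in CRF", within each group and visit. This overrides the general convention in SAP 9.2, under which "the denominators for percentages will be the number of participants in each intervention group with non-missing data for the variable of interest" unless a section says otherwise.

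Swabs can end early by design. Footnote 3 of Protocol Table 1 says: "Discontinue collection during hospitalization and/or per physician's discretion when two consecutive negative results are available at any time during the study". Protocol 9.4.1 and the schedule in SAP Appendix 1 carry the same rule. Two consecutive negatives are also how Protocol Table 3 and SAP Table 1 define viral clearance.

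SAP 9.5 states: "Statistical methods to address missing data for efficacy endpoints are provided in Section 11". Section 11.3.1 contains no such method. In particular, nothing there says how to classify, at later visits, a participant whose swabs ended after two negatives.

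**The concern.** A participant who has met the trial's definition of clearance, and whose swabs are then stopped, has no later result. If the site enters those visits as not done, the participant remains in the base but can no longer be counted as negative. The better an arm clears virus, and the more readily physicians stop swabbing, the more of its cleared participants disappear from the negative row.

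The table carries more weight than an exploratory summary usually would. SAP Appendix 5 records that Version 2.0 dropped the mixed model for cycle threshold values. Virology on its own is left with this table and descriptive cycle threshold summaries, and a reader of the report will take the percentages at face value.

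**Working it through.** The documents give no swab percentages and no stopping rates, so there is no stated figure to reproduce. Every rate below is an assumption chosen to show the algebra.

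**Notation, per arm and visit.** Let p be the share truly negative, and s the share whose swabs stopped after two negatives (s ≤ p). Assume that those who stopped are still negative and that no other swabs are missing.

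- SAP rule, stopped visits coded not done: percent negative = p − s; percent positive = 1 − p.
- Available results only: percent negative = (p − s)/(1 − s); percent positive = (1 − p)/(1 − s).
- Stopped participants counted as negative: percent negative = p; percent positive = 1 − p.

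The shortfall under the SAP rule is p − (p − s) = s, exactly. Since (p − s)/(1 − s) ≤ p, the available-results version is also too low for negatives, and it is too high for positives.

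**One arm, p = 80%:**

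| s | SAP rule, % neg | SAP rule, % pos | Available only, % neg | Available only, % pos | Stopped counted as negative, % neg |
|---|---|---|---|---|---|
| 10% | 70.0 | 20.0 | 77.8 | 22.2 | 80.0 |
| 20% | 60.0 | 20.0 | 75.0 | 25.0 | 80.0 |
| 40% | 40.0 | 20.0 | 66.7 | 33.3 | 80.0 |
| 60% | 20.0 | 20.0 | 50.0 | 50.0 | 80.0 |

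**Role of discretion.** With p = 80% and 50% of participants eligible to stop, let a fraction f of those eligible actually stop. The SAP rule gives 80 − 50f: 80%, 67.5%, 55% and 30% for f = 0, 0.25, 0.5 and 1. If nobody stops, there is no error.

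**Two arms, 90% vs 80% truly negative (true difference +10 points):**

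| Stopped, by arm | SAP rule, % neg | Difference (SAP rule) | Difference (available only) |
|---|---|---|---|
| 50% vs 50% | 40 vs 30 | +10 | +20.0 |
| 40% vs 30% | 50 vs 50 | 0 | +11.9 |
| 50% vs 30% | 40 vs 50 | −10 | +8.6 |

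The distortion of the arm difference is minus the difference in stopped shares. It vanishes when both arms stop equally often. In every row the percent positive under the SAP rule is 10% vs 20%, which is correct.

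**Which visits.** Swabs fall on Days 1, 4, 8, 14, 21 and 28. Negatives at Days 4 and 8 open Days 14, 21 and 28 to the effect. Day 8 is exposed only if Days 1 and 4 were both negative.

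**Coding.** If a stopped visit is left blank, the participant drops out of both numerator and denominator, and the available-results formulas apply. Percent negative is then still too low, by less.

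**The case against.** The strongest reply is that the effect is conditional and its reach is small.

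- **Stopping is discretionary and the CRF is not shown.** Both points stand. The size runs from zero upward, and the exact shortfall of s needs the visit to be coded not done.
- **The positive row survives.** This also stands. It keeps the right direction, and the gap between the two rows and 100% shows how many swabs were not done, though not why.
- **No listed endpoint depends on this denominator.** The primary endpoint is clinical progression. Clearance combined with symptom resolution is analysed over time in SAP 11.2.2.2 and, in 11.2.3, "at any time up to and including Days 8, 14, 21, and 28 will be summarized and analyzed", so two negatives once obtained are not lost through this rule. The listed virological endpoint is virus quantity, summarised in 11.3.2. Section 11.3.1 has no test.
- **Counting stopped participants as negative has its own assumption**, namely no return to positive. That is fair, and it is why a sensitivity table is needed.

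A reader might infer three stronger things that the documents do not support. One is that the virological comparison will be reversed. That needs unequal stopping rates between arms, which are nowhere given, and it concerns the negative row only. Another is that dropping the not-done swabs would bias percent negative upward. The algebra shows that it remains too low. The third is that the study stop distorts Days 14 to 28. For participants who had reached Day 21 but not Day 35, SAP 4 says "These participants will not have further nasal swabs for PCR test", and the only scheduled swab normally left to them is Day 28. Those not yet at Day 21 are mostly outside the final efficacy set (SAP 7.1). The stop followed a calendar date, so the documents give no reason to expect an arm difference from it.

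**Conclusion.** The point holds as a minor one, limited to the percent-negative row of an exploratory table. Where stopped swabs are coded not done, the stated denominator understates percent negative by exactly the share who stopped after two negatives. This assumes that they remain negative and that no other swabs are missing. The arm difference in that row is shifted by the difference in stopped shares, so it could shrink or reverse. The −10 points against a true +10 is an illustration under assumed rates, not a forecast. Returning to the default denominator of SAP 9.2 reduces the understatement without removing it, and makes percent positive too high. Conclusions on the primary endpoint and on the cumulative clearance endpoints do not change.

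**What to change.** Add one derivation rule to SAP 11.3.1: a participant whose swabs stopped after two consecutive negatives is counted as negative at later scheduled visits, or is shown in a separate category for swabs stopped after two negatives. State how such visits are entered in the CRF.

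Report the remaining swabs not done by reason (hospitalised, missed, study stop) and by arm. They should not be removed silently: hospitalised participants lack swabs because they worsened, and if they are more often positive, dropping them would raise percent negative most in the arm with more hospitalisations. Study-stop entries will mainly affect Day 28.

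Add the available-results version as a sensitivity table, because the main rule assumes no reversion to positive after two negatives. The separate category avoids that assumption.

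The cost is one derivation rule and one extra table. The two-negative rule uses swab results already collected; the breakdown by reason depends on what the CRF records.

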11.4 Independent Data Monitoring Committee

The purpose of the IDMC is to monitor the study for safety and efficacy. The IDMC may request additional information, or a pause in recruitment and dosing, while safety data are being evaluated.

The IDMC will operate according to a charter and the structure, participants, meeting information and other details will be provided in the charter. The charter will be available prior to study start.

The IDMC will meet monthly or ad hoc, if necessary, to review safety data, and may request additional information, or a pause, while safety data are being evaluated. All procedures associated with this review will be documented.

The IDMC will review the pausing guidelines that are put in place to address medical events necessitating a pause in enrollment and in participant dosing, and trigger IDMC reviews. Therefore, these guidelines are in effect during the active enrollment and dosing period. Any of the below conditions, if identified either by the study staff, investigator, the Sponsor or the IDMC, will trigger a pause of the enrollment and pause of administration of study intervention until the IDMC has reviewed the safety data and made a recommendation on how to proceed:

1. One report of anaphylaxis with or without bronchospasm within 4 hours of taking study intervention indicative of an immediate hypersensitivity reaction to the study intervention.
2. One report of major bleeding judged as related to study intervention by the investigator.

This sponsor will set up a proper firewall to ensure that those blinded are insulated from knowledge of unblinded interim results. Participants and study staff evaluating them will not be aware of the assigned treatment groups. The laboratories performing the SARS-CoV-2 diagnostic testing will be blinded. Sponsor will be blinded throughout the study conduct.

11.5 Group Sequential Design

11.5.1 Interim Analyses

An interim analysis will only include participants who have been lost to follow-up or who have completed 28 days of follow-up at the time of the data cut. A 2-stage group sequential design

will be used to assess futility at the interim analysis using a Hwang-Shih-DeCani beta spending function at 33% of the information. If the trial does not cross the pre-specified boundaries to declare futility at the interim analysis, a final efficacy and safety analysis will occur after all participants complete the study Day 35 of follow-up. The predefined gamma parameter used will be -4 for futility, which is similar to the boundaries from the O’Brien-Fleming method (O’Brien, 1979). The lower bound for futility will be binding.

Table 7 displays the Hwang-Shih-DeCani boundary information for the group sequential design with an interim analysis for futility after approximately 200 participants complete Day 28 and a final analysis for efficacy and safety after 600 participants completed Day 35. The actual boundaries used will be based on the Hwang-Shih-DeCani spending functions that reflect the actual number of participants (i.e., the actual proportion of the information) included at the time of the interim analysis.

Table 7: Example of Alpha and Binding Beta Boundaries

| Boundary Information (p-Value Scale) [EAST 6 (Version 6.5)] Binding Beta Boundary | | | | |
|--|-------------------|------------------------|-------------------|--------------|
| Stage | Information Level | | Boundary p-values | |
| | Proportion | Number of Participants | Alpha | Binding Beta |
| Interim 1 | 0.3333 | 200 | NA | 0.7550 |
| Final | 1.0000 | 600 | 0.0250 | 0.0250 |

If the test statistic of the interim analysis for the primary endpoint crosses the pre-specified binding futility boundary to declare futility, the study will stop enrollment, but will continue following those enrolled participants until study completion. The study will not be evaluated for efficacy at the interim analysis.

